Methods: PIONEER will be a three-arm, programmatic cluster randomized controlled trial (RCT) to compare the effectiveness of the three implementation strategies, followed by a mixed-methods implementation evaluation study guided by a transformative paradigm. For the cluster RCT, we will enroll 12 diverse clinics, which will be randomly assigned to one of the intervention arms for delivering gonorrhea testing: a standard pay-it-forward implementation strategy with minimal encouragement to get tested, a community-engaged pay-it-forward strategy, and a control arm in which men pay for their own STD test. The public and MSM-led clinics in the same city will be randomized to the same study group to prevent contamination. The primary outcome of the RCT will be gonorrhea test uptake, and secondary outcomes will include chlamydia testing, STD treatment among those with infection, amount donated, 100% condom use, and antimicrobial resistance. A sequential explanatory mixed methods design will be used to evaluate the implementation process. Data sources will include survey data on the acceptability of the intervention, intervention appropriateness, feelings and attitudes towards the interventions among participants, administrative data about test uptake, treatment rate, and donations, as well as qualitative data to gain insights about men's perceptions and attitudes towards the pay-it-forward interventions strategies, mechanisms driving uptake and donating behaviors. Both survey and qualitative interviews with implementers and organizers about fidelity and adherence to protocol, intention to continue and maintain a pay-it-forward intervention, and barriers and facilitators of implementing the intervention will be conducted.

Discussion: PIONEER will substantially increase gonorrhea testing among MSM in China, providing an innovative new financial mechanism to sustain STD screening among sexual minorities in low- and middle-income countries. This study will answer compelling scientific questions about how best to implement pay-it-forward and the individual and organizational characteristics that moderate it.

Contributions to the literature

- This cluster randomized controlled trial aims to examine the effectiveness of two implementation strategies involving different levels of community engagement to translate the generosity created by the pay-it-forward approach into test-taking action.

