Pay-it-forward has a person receive a gonorrhea test as a gift from the local community and then decide to donate money to support subsequent testers (**Figure 1**)^{17,18}. Pay-it-forward fits within the broader field of behavioral economics, which uses multiple disciplines to understand human decision-making. Pay-it-forward chains of giving are sometimes driven by unconnected generous individuals¹⁸, but more often organized by a group with a common purpose^{19,20}. Studies have shown that pay-it-forward can be sustainable and promote generosity²¹.

[figure not shown]

Figure 1. Overview of pay-it-forward. *Participatory activities such as open calls to create handwritten messages in the community-engaged implementation strategy. A warm glow refers to a positive feeling after receiving a gift.

Our previous pay-it-forward research showed that it was associated with a substantial increase in gonorrhea test uptake compared to standard of care^{22,23}. However, these studies have several limitations. First, the projects were mostly, although not entirely, implemented at MSM-led clinics. These clinics serve MSM who are more likely to disclose their sexual orientation compared to MSM who present to public clinics. Alongside the MSM volunteers at MSM-led clinics, these sites are likely in a better position to organize MSM community engagement activities¹⁵. In addition to MSM-led clinics, public clinics also provide gonorrhea testing and treatment for MSM. Public clinics include HIV testing sites and STD clinics that receive support from public health authorities. Public clinics have higher rates of linkage to care and are more likely to have antibiotic therapy on-site. Second, MSM included in these two studies were mostly younger, better educated, higher income, and more willing to donate. The pay-it-forward intervention needs to be evaluated in additional cities and different types of clinics (i.e., both MSM-led and public clinics). Last, the previous study showed that pay-it-forward was effective compared to the standard of care, but explicit and intentional support for implementation is needed for scale-up. Lack of implementation evaluation limits our understanding of the implementation process, and community-engaged strategies are needed to maximize efficiency and effectiveness. These underscore the importance of implementation research to inform contextually appropriate strategies to implement pay-it-forward most effectively at scale.

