Community-engaged Pay-it-forward arm	Free gonorrhea/ chlamydia testing	Active: multi-stakeholder co-creation activities to develop essential components of the intervention and implementation strategies; writing postcards; designing fans with stickers,; sending out testing promotion messages on social media; an opportunity to donate to support others.
Control arm	Fee-based gonorrhea/ chlamydia testing (approximately 20 USD)	None

*Note: All participants who test positive for gonorrhea will receive a referral for AMR testing and treatment at the local public STD clinic.

In the standard strategy/arm, MSM who enter the clinic will be provided with a free gonorrhea test alongside handwritten postcards from other MSM in the local community. Our previous RCT has already created standard operating procedures, survey instruments, and educational materials for this intervention. The initial postcards were generated through an open call for suggestions about tailored, handwritten messages that are clinic-specific and locally appropriate. We used the standardized methods developed by the World Health Organization to design the open call. Briefly, this will involve creating a steering committee, promoting the open call, judging submissions, recognizing excellent submissions, and implementing selected ideas.

In contrast, the community-engaged strategy/arm will include all elements of the standard strategy, in addition to the following key components: gift recipients will be invited to select a handwritten postcard for keepsakes, submit handwritten postcards of their own, draw on and decorate plain hand fans with stickers, send out messages promoting gonorrhea/chlamydia testing on social media platforms, or create videos promoting gonorrhea testing (to be viewed at the same clinic). Men who agree to participate in the community-engagement activities will be invited to a pay-it-forward event where they will meet other people who have donated, and will also be invited to related participatory activities organized by the local clinic to promote gonorrhea testing.

In the control arm, MSM will be informed about the importance of gonorrhea testing but will not receive handwritten postcards or other community engagement activities. Among men who choose to receive gonorrhea testing, they will have access to the same diagnostics,

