Figure 2 shows the cluster RCT design flowchart. We will assign clinics to study arms on a 1:1:1 basis using covariate-constrained randomization. We will use covariate-constrained randomization to decrease potential bias associated with unbalanced study arms. We will balance the number of MSM-led and public clinics in each arm because these are unique implementation structures. All men recruited via one clinic will be assigned to one arm. We will recruit and screen men until we meet our sample size of 1200 men.

[figure not shown]

Figure 2. Pragmatic RCT flowchart. Each city will have one MSM-led clinic and one public clinic participating.

Intervention delivery strategies

The duration of the intervention is one year at each clinic, with the potential to continue based on local commitments. All patients who accept testing will receive gonorrhea/chlamydia PCR testing. This diagnostic is approved by the US FDA and the Chinese national regulatory authority. Men who agree to be tested will have specimens collected from

pharyngeal, rectal, and urethral sites. Specimens will be pooled based on excellent sensitivity and specificity. Turnaround time for test results will depend on the local clinic. Surveys will be done online in order to facilitate implementation. All participants diagnosed with gonorrhea will receive ceftriaxone and azithromycin in accordance with WHO recommendations for first-line gonorrhea therapy.

Outcome measures

The primary outcome of the RCT will be gonorrhea test uptake ascertained by administrative review from participating clinics. We used this same primary outcome in previous quasi-experimental and RCT trials evaluating pay-it-forward. Secondary outcomes will include syphilis testing, amount donated towards pay-it-forward, antimicrobial resistance measures, positive tests for gonorrhea and chlamydia, measures of gratitude and community solidarity, and per unit costs associated with the intervention (Table 2).

Table 2. Secondary outcomes of the cluster RCT			
Outcome	Time Frame	Ascertainment	Data Analysis
Primary			
Gonorrhoea and Chlamydia test uptake		Clinic administrative data	Generalized mixed effects models (compare control arm to pay-it-forward intervention)
Secondary			
Amount donated	During enrollment visit	Administrative data	Descriptive analysis
The number of participants who tested positive for Gonorrhea	During enrollment visit	Laboratory result	Descriptive analysis

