The number of participants tested positive for chlamydia	During enrollment visit	Laboratory result	Descriptive analysis
The proportion of those who tested positive for Gonorrhea or Chlamydia who returned for referral treatment	One month after receiving the results	Self-reported follow-up survey (linkage to care, treatment)	Descriptive analysis
Cost per test ¹	During enrollment visit	Costing data collection	Micro-costing approach

Adapted gratitude scale	During enrollment visit	Self-report	T-test
Community solidarity scale ⁴	During enrollment visit	Self-report ²	T-test
Community cohesion	During enrollment visit	Self-report	T-test
Internalized homophobia	During enrollment visit	Self-report	T-test
Subgroup analysis			
Gonorrhea and chlamydia testing uptake by clinic type	During enrollment visit	Administrative data at study site	MSM-led clinic vs. public STD clinic
Gonorrhea and chlamydia testing uptake by sexual orientation	During enrollment visit	Self-reported sexual orientation data from baseline survey	Self-identified sexual minority vs. not
Gonorrhea and chlamydia testing uptake by age group	During enrollment visit	Self-reported socio-demographic data from baseline survey	≤30years vs. >30years
Gonorrhea and chlamydia testing uptake by PrEP eligibility	During enrollment visit	Self-reported frequency of condom use in during sexual intercourse in the past 3 months data from baseline survey	Condom use vs. Condomless sex.

¹Cost per test is defined as the cost associated with respective interventions (development, start-up, implementation, intervention) per individual who reported testing for gonorrhea and chlamydia following the intervention; economic test and financial cost are reported separately.
 
²Community solidarity involves engagement, social network support, and a sense of belonging. These items were used in our previous pay-it-forward research study..
			

Data analysis

Data will be analyzed using a transformative mixed method research approach. The primary outcome will be gonorrhea and chlamydia test uptake among MSM. Quantitative and qualitative data will be analyzed using a convergent parallel design (i.e., analyze quantitative

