Thematic analysis will be used to analyze qualitative data. A codebook will be developed by a senior qualitative researcher. Two research assistants will then code the transcripts based on the codebook. NVivo version 12 (NVivo, Columbus, OH) will be used for qualitative data analysis. Descriptive data analyses, independent sample t-tests and chi-square tests will be used to compare differences in RE-AIM measures between pay-it-forward and standard-of-care arms. We will generate a global implementation score and scores of separate dimensions and convert them to a z-score. Correlates of global implementation and implementation dimensions will be examined using general linear mixed models (GLMM). In addition, qualitative data on social networks will be applied to disentangle the connection between an individual's gratitude and position within a network comprised of helping relationships (both direct and indirect relationships). Finally, we will use linguistic inquiry word count to analyze textual information gathered as part of community engagement activities.

Safety management plan

Criteria for withdrawal: if participants want to quit the study for any reason. Project implementers will do data and safety monitoring.

Data management information

For the surveys and demographic questionnaires, all data are directly entered into computers at the UNC Project China office as participants complete the surveys. Programs to ensure accuracy, completeness, and internal consistency are automated. Data can be readily downloaded and converted to the format of commercially available statistical software. During the collection of the online portion of the study, all data will be transmitted securely using SSL (TLS) 128-bit encryption across the Internet (HTTP). SSL provides users with the assurance of access to a valid, "non-spoofed" site, and prevents data interception or tampering with sensitive information. The SSL certificate that will be used for this project will

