use 128-bit encryption, the preferred security level of government and financial institutions. 128-bit encryption offers protection that is virtually unbreakable. For example, if a hacker could crack a standard 40-bit SSL session in a day, it is estimated that it would take well beyond a trillion years to accomplish the same thing against a 128-bit SSL session. A dedicated server, which eliminates security issues involved with shared hosting environments where hundreds of websites and users reside on one shared web server as well as ensuring both physical and network security, will be used to house the data. Data will then be stored in a secured server at Dermatology Hospital, Southern Medical University. The server will be configured with a redundant hard drive array to ensure reliability. Access to the data will be password-protected within the server's firewall. Only the PI and a designated senior staff member will have the password to access the "key" that links the non-descript identifier to personally identifiable information. IP addresses of participant's computers will not be collected at any time. Cookies will not be used in any way to track participant activity. A quick link will exist on each survey page to provide participants with a rapid way to switch to an innocuous website if their privacy is interrupted while completing the survey.

For participants' urine testing results and clinical outcomes, the data will be recorded directly and input into the Health Information System (HIS) at the public STD clinic. Data will be downloaded and stored the same way as the survey data.

Table 3. Dimensions of RE-AIM in implementation research adapted for pay-it-forward.³¹

Dimensions	Level	Operational definitions	Measurement method	Analysis
Reach	Individual	
 Proportion of MSM who enter the clinic and are screened for eligibility Percent of MSMs who visit the clinic compared to the MSM in the catchment area 	RCT data Local CDC data	Descriptive analysis
Effectiveness	Individual	
 How effective are the two implementation strategies in promoting gonorrhea test uptake? Does pay-it-forward influence secondary outcomes (chlamydia testing, treatment and prevention outcomes)? 	RCT data	Covered in RCT analyses above

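### The only treatment outcome is a proportion among men who tested positive, a group shaped by allocation, so it cannot answer the Table 3 question whether pay-it-forward influences treatment

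*Combined protocol and SAP*

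**What the plan says.** Table 2 has one treatment outcome: "The proportion of those who tested positive for Gonorrhea or Chlamydia who returned for referral treatment". It is ascertained by "Self-reported follow-up survey (linkage to care, treatment"), one month after results, and its analysis is given as descriptive. The abstract conditions in the same way: "STD treatment among those with infection". Table 2 also lists, descriptively, the numbers positive for gonorrhea and for chlamydia.

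The section on intervention delivery strategies states: "All patients who accept testing will receive gonorrhea/chlamydia PCR testing". Only men who accept can therefore be found positive, and acceptance is the primary outcome. Table 1 gives both pay-it-forward arms a free test and the control arm "Fee-based gonorrhea/ chlamydia testing (approximately 20 USD").

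The Effectiveness row of Table 3 asks: "Does pay-it-forward influence secondary outcomes (chlamydia testing, treatment and prevention outcomes")? It names RCT data as the source and says that the RCT analyses already cover the question. Under the implementation evaluation, the data analysis section plans t-tests and chi-square tests to "compare differences in RE-AIM measures between pay-it-forward and standard-of-care arms".

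No treatment outcome over all enrolled men is defined, and the plan does not discuss how men come to be in the test-positive group.

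**The concern.** The Table 3 question is causal: does allocation to pay-it-forward change treatment? Randomising clinics supports an answer when the denominator is all enrolled men in each arm. It does not when the denominator is a group selected after allocation by a step that the intervention targets. Men who test because the test is free and promoted may differ in infection risk and in readiness to return from men who would pay. If they return less often, the proportion treated among positives falls even though no man is treated less and more infections are treated in total.

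At stake is a secondary conclusion. A report could say that pay-it-forward weakens linkage to treatment, or makes no difference to treatment, when it led to more men being treated.

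**Working it through.** **Inputs from the plan.** There are 1200 men in 12 clinics, 100 per clinic, allocated 1:1:1 (sample size and randomization sections), so 1200 / 3 = 400 men per arm. The Background reports gonorrhea prevalence in MSM in southern China of up to 12.5%. It also reports, from earlier work, a "substantial increase in gonorrhea test uptake compared to standard of care", without a rate.

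**Not in the plan.** Uptake by arm and the proportion treated are not given, and the plan has no figure for treatment to reproduce. All such rates below are assumptions. Positivity is set at 12.5% and, as an assumed lower value, 5%.

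**Formulas, per arm**, with uptake u, positivity among testers p and proportion of positives treated t:
- positives = 400 × u × p
- treated = positives × t
- Table 2 measure = treated / positives = t
- all-enrolled measure = treated / 400 = u × p × t

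**Step 1: selection alone.** Assume uptake of 20% (control) and 50% (pay-it-forward), and p = 12.5%. Men who would test anyway are treated 90% of the time in either arm; the extra testers, 60%.
- Control: 400 × 0.20 × 0.125 = 10 positives; 10 × 0.90 = 9 treated.
- Pay-it-forward: the same 10 positives with 9 treated, plus 400 × 0.30 × 0.125 = 15 positives with 15 × 0.60 = 9 treated. Total: 25 positives, 18 treated.

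| Measure | Control | Pay-it-forward |
|---|---|---|
| Treated / positives | 9/10 = 90% | 18/25 = 72% |
| Treated / enrolled | 9/400 = 2.25% | 18/400 = 4.5% |

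The first row favours control by 18 points; the second favours pay-it-forward twofold.

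**Step 2: fewer infections among the extra testers.** With 6% positivity in that group, 400 × 0.30 × 0.06 = 7.2 further positives and 7.2 × 0.60 = 4.32 further treated. The proportions are 90% and 13.32/17.2 = 77%; the men treated are 9.0 and 13.3. The direction is unchanged.

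**Step 3: when the signs disagree.** If p is equal in both arms, the two measures disagree whenever t(control) × u(control)/u(PIF) < t(PIF) < t(control). With 20% v 50% uptake and 90% treated in control, the lower limit is 0.90 × 0.20/0.50 = 36%, so any pay-it-forward value between 36% and 90% gives opposite signs.

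**Step 4: range of assumptions.** Two positivities (5%, 12.5%), four uptake pairs (20 v 30%, 20 v 50%, 30 v 50%, 20 v 60%) and three pairs for treatment among positives (90 v 70%, 90 v 80%, 80 v 60%) make 24 scenarios. The signs are opposite in all 24, because every one lies inside the limits of step 3. With equal treatment (80% in both arms), 20 v 50% uptake and 12.5% positivity, the Table 2 measure shows no difference while men treated per 100 enrolled rise from 2.0 to 5.0.

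**Step 5: precision, ignoring clustering.** Exact 95% intervals in step 1 are 55 to 100% for 9/10 and 51 to 88% for 18/25, with about 16% power for that contrast. For the all-enrolled measure they are 1.0 to 4.2% and 2.7 to 7.0%. Neither measure is precise.

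**The case against.** The strongest reply is that no inferential comparison of arms is planned on this row. Table 2 marks it descriptive, and the mixed models are tied to test uptake. That stands. A reader might infer from the chi-square tests in the implementation evaluation that the proportion among positives will be formally tested between arms. The documents do not support this: Table 3 assigns the Effectiveness row to the RCT analyses, and the outcome section of the implementation evaluation describes the RE-AIM comparison as one between the two pay-it-forward strategies. What remains is that Table 3 asks a causal question and sends the reader to a row that cannot answer it.

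Other points also stand in part:
- The proportion among positives is a legitimate measure of linkage to care. The all-enrolled figure is a product that includes uptake, and on its own it could hide a real fall in linkage. This argues for reporting both.
- The counts of positives in Table 2 would let a careful reader approximate the number treated. The approximation is not planned, the two counts overlap in men with both infections, and survey non-response is not addressed.
- The free-versus-fee mechanism applies only to pay-it-forward against control. Between the two pay-it-forward arms, both free, selection would have to come from any difference in uptake that the engagement activities produce.
- The rates in the illustration are assumed, and nothing in the documents shows that men drawn in by a free test return less often. The 12.5% is an upper figure for gonorrhea in MSM, whereas public clinics recruit all men and the outcome also covers chlamydia.

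**Conclusion.** The concern holds as a mismatch between question and measure. Allocation shapes the test-positive group through uptake, so a difference between arms in the proportion treated among positives is not a randomised comparison and can have the opposite sign to the difference in men treated. In the worked case the gap is 90% v 72% against pay-it-forward, beside 2.25% v 4.5% of enrolled men in its favour.

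A reader might go further and infer that the measure will mislead, or that the intervention wholly creates the test-positive group. Neither follows. The sign reverses only if treatment among positives is lower under pay-it-forward but above the limit in step 3, and the plan has no data on this. Some control men will also test and be positive.

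The point concerns a secondary outcome and leaves the primary analysis of uptake untouched. It is worth correcting before analysis because Table 3 presents treatment as an effectiveness question.

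**What to change.** Add one secondary row to Table 2: tested positive for gonorrhea or chlamydia and treated, out of all enrolled men, by allocated arm and allowing for clinic clustering. Name it in Table 3 as the answer to the treatment question. For this row:
- Count each man once, whether he has one infection or both.
- State the data source. Table 2 uses a self-report survey, the data collection section lists the treatment rate among administrative data, and the data management section records clinical outcomes in the clinic information system. These need to be reconciled.
- Count positives with no record of treatment as untreated, with a sensitivity analysis for that rule.

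Keep the proportion among positives as a description of linkage to care within each arm, and say that it is not a randomised comparison.

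The cost is one table row, the source and missing-record rules, and a sentence in Table 3. It relies on data that the plan already intends to collect and changes no clinical procedure. The downside is few events: roughly 10 to 20 per arm in the step 1 illustration, and about 3 to 10 in the 5% positivity scenarios. With four clinics per arm, a clustered estimate will be imprecise and a model may be unstable. Because the figure partly reflects uptake, it should be reported beside the linkage row.

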Mixed methods will be used to evaluate the implementation process with project implementers, organizers, and participants. Data sources will be multiple, which will include survey data on the acceptability of the intervention, intervention appropriateness, feelings and attitudes towards interventions among participants, administrative data about test uptake, treatment rate, and donations, as well as qualitative data to gain insights about men's perceptions and attitudes towards the pay-it-forward interventions strategies, mechanisms driving uptake and donating behaviors. Both survey and qualitative interviews with implementers and organizers about fidelity and adherence to protocol, intention to continue and maintain a pay-it-forward intervention, and barriers and facilitators of implementing the intervention will be conducted.

Study setting and population

We will implement the study in Guangdong cities with either (or both) public STD and MSM-led clinics. Examples include Zhuhai, Foshan, Jiangmen, Zhanjiang, Zhanjiang, Dongguan, and Huizhou. These clinics were chosen because respective cities have a higher burden of STDs, and findings would be potentially relevant in many cities. In MSM-led clinic, only MSM who

meet eligibility criteria will be included. In public STI clinics, all men will be recruited. The rationale for this is that many MSM do not identify as being attracted to other men.

The study settings between public clinics and MSM-led clinics would be different. One key obstacle to recruiting MSM at public STD clinics is that MSM usually may not want to disclose their sexual identities due to justifiable fears about risks of stigma and discrimination from other men and health workers. Therefore, to avoid indirect sexual orientation disclosure and feelings of discrimination, public STD clinic recruitment will be extended to include all men visiting the public clinic setting regardless of sexual orientation. This will lower the risk of being unnecessarily 'targeted' and accidental sexual orientation disclosure.

The inclusion criteria at public clinics include men who are at least 18 years old; have had sex over the past year; have not been tested for gonorrhea and chlamydia in the past year; reside in the city in the past three months; speak Mandarin Chinese or Cantonese; mentally capable of providing informed consent to test for gonorrhea and chlamydia; and owning a mobile phone.

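### Return for referral treatment is taken only from a self-reported one-month survey, with no rule for non-responders, although the protocol elsewhere treats it as clinic data

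*Combined protocol and SAP*

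**What the plan says.** Table 2 lists as a secondary outcome "The proportion of those who tested positive for Gonorrhea or Chlamydia who returned for referral treatment". Its time frame is "One month after receiving the results", its ascertainment is "Self-reported follow-up survey (linkage to care, treatment"), and its analysis is descriptive. No clinic record is named as a source, cross-check or fallback.

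Other parts of the protocol describe clinic data on treatment or on clinical outcomes:

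- The abstract and the Data collection section both list "administrative data about test uptake, treatment rate, and donations" among the data sources.
- The note to Table 1 reads "All participants who test positive for gonorrhea will receive a referral for AMR testing and treatment at the local public STD clinic".
- Data management information states that, for participants' urine results and "clinical outcomes, the data will be recorded directly and input into the Health Information System (HIS) at the public STD clinic". It continues: "Data will be downloaded and stored the same way as the survey data".

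The section on intervention delivery says that surveys are done online. The protocol gives no target response for the follow-up survey, no rule for counting men who do not answer, and no missing-data method for this outcome.

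**The concern.** The outcome is an event at a clinic: a man who tested positive came back for treatment on referral. Table 2 takes the comparable items (uptake, donations, test results) from administrative or laboratory data. This outcome is the exception, and the only one in Table 2 with a stated time frame after the enrollment visit, so it is the most exposed to loss to follow-up.

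Two errors can enter. Men who returned may answer the survey at a different rate from men who did not, and some men may report treatment that they did not receive. In addition, the outcome is defined over all men who tested positive, whereas a survey observes only responders. The stated proportion therefore cannot be computed without a further assumption, and the plan gives none.

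At stake is the trial's account of treatment after diagnosis. The abstract names treatment as a secondary outcome, and the effectiveness row of Table 3 asks whether pay-it-forward influences it.

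**Working it through.** The plan gives no expected treatment rate, survey response rate or reporting accuracy, so there is no figure of its own to reproduce. All rates below are assumptions chosen to show scale, except the 12.5% prevalence and the sample size.

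**1. Selective response.** Let t be the true proportion who returned, and r1 and r2 the response rates in treated and untreated men.

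- Non-responders dropped: t·r1 / (t·r1 + (1 − t)·r2)
- Non-responders kept and counted as not returned: t·r1

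With t = 0.60:

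| r1 / r2 | Dropped | Counted as not returned |
|---|---|---|
| 80% / 50% | 0.48 / (0.48 + 0.20) = 71% | 48% |
| 90% / 40% | 0.54 / (0.54 + 0.16) = 77% | 54% |
| 80% / 80% | 0.48 / (0.48 + 0.32) = 60% | 48% |

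The same survey data overstate the rate under one rule and understate it under the other. Equal response removes the error only if non-responders are dropped.

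**2. Bounds without assuming who responds.** With non-response r and proportion p among responders, the proportion of all test-positive men reporting or having treatment lies between (1 − r)·p and (1 − r)·p + r, taking responders' answers as true. In the first row above, r = 1 − 0.68 = 0.32, and the bounds are 48% and 48% + 32% = 80%. In general the width equals the non-response. At p = 70%, non-response of 10%, 20%, 30% and 40% gives 63–73%, 56–76%, 49–79% and 42–82%.

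**3. Misreporting.** If everyone answers and a share f of untreated men report treatment, the survey shows t + (1 − t)·f. For t = 0.60 and f = 5%, 10% and 20%, this is 62%, 64% and 68%.

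**4. Number of men.** The sample size section gives 1,200 men over three arms, or 400 per arm. The Background gives a gonorrhea prevalence of up to 12.5% among MSM in southern China. Assuming uptake of 20%, 50% or 80%, gonorrhea positives per arm are 400 × uptake × 0.125 = 10, 25 or 40, before chlamydia-only positives are added. One man with unknown status is then 10, 4 or 2.5 percentage points of those counts.

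**5. The passages side by side.** Treatment rate is administrative in the abstract and in Data collection, and self-reported in Table 2. The Table 1 note sends gonorrhea-positive men to the local public STD clinic, and Data management has clinical outcomes entered in that clinic's system and extracted. The plan therefore points to a second source, but Table 2 does not use it.

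**The case against.** The strongest reply is that usable clinic records of this event are not guaranteed. Four parts of it stand:

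- Data management refers to clinical outcomes and does not name treatment. Treatment rate, where it is called administrative, is listed as a source for evaluating implementation, and nothing says that it is an individual record linked to a participant.
- The referral note covers gonorrhea only, while the outcome includes chlamydia.
- By the caption of Figure 2, each city has one MSM-led and one public clinic. No procedure is given for linking men recruited at an MSM-led clinic to the public clinic's system.
- Clinic records miss treatment obtained elsewhere, for which a survey is a reasonable source.

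These points call for checking coverage and keeping the survey. They do not justify leaving Table 2 in conflict with the other sections, or leaving non-response without a rule.

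A reader might infer that the survey must overstate treatment. The documents do not support that, because it requires dropping non-responders, and the plan does not say so. A reader might also infer a bias between arms, since the community-engaged arm has more contact with the clinic. Those extra activities are by invitation, and nothing in the documents shows how survey response would vary by arm. Nor do the documents show that men who do not return are less likely to answer. That is plausible but remains an assumption.

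**Conclusion.** The point holds as an inconsistency about the data source combined with a missing rule for non-response. The outcome is open to error from non-response and misreporting. The size cannot be estimated from the documents, and the direction depends on the unstated rule: 71% or 48% against an assumed true 60%, at assumed response rates of 80% and 50%. Any difference between arms is undetermined.

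The consequence is limited. The outcome is secondary and analysed descriptively, and the primary outcome already rests on clinic administrative data. The change is worth making because it is cheap and largely frees an outcome defined as return to a clinic from dependence on who answers a survey.

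**What to change.** Reconcile Table 2 with the abstract, Data collection and Data management information as follows:

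1. Name the referral clinic's information-system or administrative record, within one month of the result, as the main source. State that the denominator is all test-positive men.
2. Keep the survey as a supplement. Report treatment received elsewhere separately, so that the outcome remains return for referral treatment.
3. Report survey response, and agreement between the two sources, by arm.
4. For men with neither source, give bounds, counting them once as not treated and once as treated. Counting them only as not treated would bring a downward bias of its own wherever linkage fails.
5. Confirm that the clinic system records treatment and covers chlamydia-only positives and men recruited at MSM-led clinics. Where it does not, keep the survey as the source with the same bounds.

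The cost is a change of wording in Table 2 and some record linkage, which will be more work for MSM-led sites. No new visits are needed. Treatment obtained elsewhere will still be missed for men who do not answer the survey.
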